12.5 Adverse Event Reporting Period -

Adverse events of **grades 3-5** will be monitored and recorded in study-specific case report forms (CRFs) throughout the investigative phases of the study: during and for 48 hours after leukapheresis and then from the start of interferon gamma through day 28 after each T cell infusion. Additionally, grade 1-2 adverse events will be monitored and recorded from the start of T cell infusion through day 28 after each T cell infusion. Adverse events will continue to be monitored and recorded in conjunction with standard follow-up time points during the first year following T cell infusion. The detailed collection of AEs will stop at the time of commencement of new anti-tumor therapy.

AEs with an onset date prior to apheresis will not be recorded, except in the case of clinically significant worsening of the AE during the specified monitoring time frame. A patient withdrawn from the study

because of an adverse event must be followed until the clinical outcome from the adverse event is determined.

The following events are *not* identified as AEs in this study:

- Disease progression or relapse.
- Hospitalization for the purpose of facilitating T cell infusion is not considered an AE. Any AE requiring prolongation of this hospitalization will be recorded and patient to applicable SAE reporting.
- Medical or surgical procedures in and of themselves, including those that require hospitalization (e.g., surgery, endoscopy, biopsy procedures) are not considered AEs. However, an event or condition requiring such procedures may be an AE.

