2.2.3 Interferon gamma- safety and clinical results

Interferon gamma is FDA-approved for the treatment of chronic granulomatous disease at a dosage of 50mcg/m² given three times weekly, and is generally tolerated with the known common (>10%) side effects of fever, headache, chills, fatigue, rash, diarrhea, vomiting and injection site reactions. The peak concentration of interferon gamma occurs in 7 hours and is 0.6ng/ml in plasma, with a half-life of 6 hours. Importantly this concentration is associated with significant class I MHC upregulation in Merkel cell carcinoma cells *in vitro* (Figure 10B). Use of subcutaneous interferon gamma in cancer patients has been explored in a previously reported phase 0 trial conducted in sarcoma patients.⁶³ In this trial, administration of interferon gamma was well tolerated and resulted in upregulation of class I MHC in patient tumors and increases in measures of tumor inflammation. Interferon gamma at standard dosing has been given in combination with the PD-1 inhibitor nivolumab in a phase I clinical trial of over 20 patients with no evidence of increased immune related adverse events related to nivolumab (no cases of

grade III or greater immune toxicity during combination treatment) or potentiation of side effects from interferon gamma ([name], personal communication, manuscript in preparation).

2.3 Rationale for administration of TCR-transgenic T cells in the context of treatment with avelumab or Pembrolizumab as a standard of care

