6.3 Interferon Gamma treatment

Interferon gamma is being administered with the goal of upregulation of class I MHC on Merkel cell carcinoma cells to allow recognition of tumor cells by TCR transgenic T cells. Interferon gamma (Actimmune) will be administered at the FDA-approved dosing (for the indication of chronic granulomatous disease) of 50mcg/m² given subcutaneously in the abdomen, anterior thigh, or deltoid region three times weekly, starting 5-7 days prior to the T cell infusion and continuing for a total of 4 weeks. Patients will receive premedication with acetaminophen prior to each dose to minimize flu-like symptoms. Doses will be held if creatinine rises above 2.0; creatinine will be monitored by regular comprehensive metabolic panels per **Appendix A**.

Dose reduction or skipping, as clinically required in the event of adverse events is permissible at the discretion of the PI or designee.

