6.4.2 T Cell Infusions

1. TCR-T cells should be administered approximately 5-7 days after the initiation of *interferon gamma*. A window of 4-8 days is acceptable if a 5-7 day window is not possible for logistical reasons.
2. On the day of scheduled T cell infusion, the patients should undergo a clinical evaluation and a clinical determination for appropriateness to proceed with T cell administration.
3. Patients deemed not appropriate for T cell administration may receive a T cell infusion outside the specified window if they subsequently resolve the clinical and/or laboratory concerns which deemed them inappropriate within 60 days of the planned initial infusion. In these cases, the product will be frozen and thawed on the new day of administration, as per facility policy and procedures.

4. Patients who are unable to undergo TCR-T cell infusion within the intended window due to manufacturing or release issues may receive the cell infusion outside of this window if the issues can be resolved. Discussion with the protocol PI and notification of IND holder is required.

FH-MCVA2TCR will be provided as a single cell product at the assigned cell dose.

The final product will be prepared and labeled according to standard operating procedure in the Cellular Processing Facility. The cell product will be transported to the infusion facility by a delegated staff member. During the time of transportation, the cell product will be kept in a cooler with a cool pack. A nurse will then administer the cells using standard/universal institutional precautions for blood borne pathogens.

All patients will be monitored during each T-cell infusion with vital signs and O₂ saturation being recorded (+/- 5 minutes) within 15 minutes prior to the start of infusion, at thirty-minute intervals during, at completion of the infusion, and hourly after the infusion for at least 2 hours after the infusion.

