11.7 Participant discontinuation of active treatment

A patient will no longer be able to receive active treatment on study (T cells, avelumab or pembrolizumab, or class I MHC upregulation) for any of the reasons listed below.

- Progressive disease or development of new metastasis requiring urgent change in treatment after the second T cell infusion. Patients with progressive disease on 4 week imaging but clinical stability may remain on study given the possibility of pseudoprogression and delayed clinical responses to immunotherapy.
- The participant withdraws consent
- Patient death
- Occurrence of pregnancy
- Participation in another therapeutic trial during the treatment duration of this trial
- Occurrence of an exclusion criterion, which is clinically relevant and affects the subject's safety, if discontinuation is considered necessary by the Investigator or Sponsor
- A patient will no longer be eligible to receive additional therapy if the PI or his designee determines that additional T cell infusions are not in the best interest of the patient
- Occurrence of any non-pre-existing grade 3 or higher AEs / repetitive Grade 2 Adverse events deemed related to the treatment, except for expected, transient toxicities associated with avelumab, pembrolizumab, interferon gamma and T cell infusion.

- Cytokine release syndrome requiring pressors for >24 hours or tocilizumab
- The reasons for premature discontinuation must be recorded on the case report form. The patient may re-enter the study after premature discontinuation only by approval of the PI

Unless there is withdrawal of consent or death, the patient will transition to the LTFU phase of study.

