APPENDIX E: CRS and Neurotoxicity Grading Criteria

ASTCT CRS Consensus Grading

CRS Parameter	Grade 1	Grade 2	Grade 3	Grade 4
Fever*	Temperature $\geq 38^{\circ}\text{C}$	Temperature $\geq 38^{\circ}\text{C}$	Temperature $\geq 38^{\circ}\text{C}$	Temperature $\geq 38^{\circ}\text{C}$
With				
Hypotension	None	Not requiring vasopressors	Requiring a vasopressor with or without vasopressin	Requiring multiple vasopressors (excluding vasopressin)
And/or [†]				
Hypoxia	None	Requiring low-flow nasal cannula [‡] or blow-by	Requiring high-flow nasal cannula [‡] , facemask, nonrebreather mask, or Venturi mask	Requiring positive pressure (eg, CPAP, BiPAP, intubation and mechanical ventilation)

Organ toxicities associated with CRS may be graded according to CTCAE v5.0 but they do not influence CRS grading.

* Fever is defined as temperature $\geq 38^{\circ}\text{C}$ not attributable to any other cause. In patients who have CRS then receive antipyretic or anticytokine therapy such as tocilizumab or steroids, fever is no longer required to grade subsequent CRS severity. In this case, CRS grading is driven by hypotension and/or hypoxia.

[†] CRS grade is determined by the more severe event: hypotension or hypoxia not attributable to any other cause. For example, a patient with temperature of 39.5° C, hypotension requiring 1 vasopressor, and hypoxia requiring low-flow nasal cannula is classified as grade 3 CRS.

[‡] Low-flow nasal cannula is defined as oxygen delivered at ≤ 6 L/minute. Low flow also includes blow-by oxygen delivery, sometimes used in pediatrics. High-flow nasal cannula is defined as oxygen delivered at > 6 L/minute.

CRS grading will be as per ASTCT CRS Consensus Grading. Table reprinted for reference from the guideline of Lee et al, 2019 ASTCT Consensus Grading for Cytokine Release Syndrome and Neurologic Toxicity Associated with Immune Effector Cells, Biol Blood Marrow Transplant 25(2019) 625-638

ASTCT ICANS Consensus Grading for Adults

Neurotoxicity Domain	Grade 1	Grade 2	Grade 3	Grade 4
ICE score*	7-9	3-6	0-2	0 (patient is unarousable and unable to perform ICE)
Depressed level of consciousness[†]	Awakens spontaneously	Awakens to voice	Awakens only to tactile stimulus	Patient is unarousable or requires vigorous or repetitive tactile stimuli to arouse. Stupor or coma

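### Grade 1-2 adverse events are recorded from the T cell infusion, not from the first interferon gamma dose 5-7 days earlier, so the only interferon-alone period has no required low-grade record

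*Combined protocol and SAP*

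**What the plan says.** Section 12.5 sets two windows. Grade 3-5 events are recorded around leukapheresis and then "from the start of interferon gamma through day 28 after each T cell infusion". For the lower grades, "grade 1-2 adverse events will be monitored and recorded from the start of T cell infusion through day 28 after each T cell infusion". A further sentence covers the longer term: "Adverse events will continue to be monitored and recorded in conjunction with standard follow-up time points during the first year" after infusion, with no grade limit stated.

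Section 6.3 gives interferon gamma three times weekly, "starting 5-7 days prior to the T cell infusion and continuing for a total of 4 weeks". Section 6.4.2 adds some tolerance: "A window of 4-8 days is acceptable if a 5-7 day window is not possible for logistical reasons". Section 6.1 classes interferon gamma as investigational alongside the T cells, and the synopsis lists it as a test product. Section 6.5.2 places the first avelumab dose about 14 days after the infusion.

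Section 2.2.3 lists, as effects seen in more than 10% of patients, "side effects of fever, headache, chills, fatigue, rash, diarrhea, vomiting and injection site reactions". Appendix E defines CRS fever as a temperature of at least 38°C "not attributable to any other cause".

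**The concern.** The lead-in is the only scheduled part of cycle 1 in which interferon gamma is given without T cells or on-study checkpoint inhibitor. The plan values this kind of separation elsewhere: the closing paragraph of 13.2.2 says that delaying the checkpoint inhibitor by 14 days helps to tell its toxicity apart. For interferon the separation exists in the schedule, but its low-grade events need not be recorded.

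Interferon continues after the infusion, so its fever and CRS fever can occur in the same days. Under 12.3, fever that fits the picture of CRS is graded within CRS and not counted as a separate event. A record of fever after interferon doses given before any T cells would be the most direct within-patient evidence on whether another cause explains a later fever, which is the question Appendix E poses. At stake are the description of interferon's low-grade tolerability in these patients and the support for attributing low-grade fever after infusion.

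**Working it through.** **1. Length of the gap.** Grade 3-5 recording starts on day -7 to -5 (day -8 to -4 with the 6.4.2 tolerance). Grade 1-2 recording starts on day 0. The gap is 5-7 days, or 4-8 at the limits.

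**2. Doses in the gap.** Three times weekly for 4 weeks is 3 × 4 = 12 doses. I laid these on a Monday/Wednesday/Friday calendar, started on each of the three days, and counted doses before day 0:

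| Lead-in (days) | Doses before day 0 | Lead-in as share of 28 days |
|---|---|---|
| 4 | 2 | 14% |
| 5 | 2-3 | 18% |
| 6 | 3 | 21% |
| 7 | 3 | 25% |
| 8 | 4 | 29% |

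This reproduces the plan's own figure: footnote k of Appendix A places the pre-infusion biopsy after 2-4 interferon doses (read here as interferon gamma, the only interferon given). The share of doses is 2/12 = 17% to 4/12 = 33%. The other 8-10 of 12 (67-83%) fall on or after day 0, the last on about day +17 to +22, inside the grade 1-2 window.

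Footnote h of Appendix A runs interferon through day 28. If that counts from the infusion, the course is 33-35 days and the lead-in is 5/33 = 15% to 7/35 = 20% of it. Sections 6.3 and Appendix A must be reconciled on duration; the length of the gap in days is the same either way.

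**3. Cycle 2.** Section 6.4.4 allows a second cycle from 6 weeks. Taking that as day 42, an 8-day lead-in starts on day 42 - 8 = 34, after the first 28-day window has closed. Only the first-year sentence can cover it, and that ties recording to standard follow-up time points.

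**4. Possible size.** The documents give only a frequency above 10%, not specific to the lead-in. Assume a proportion p of patients has a given low-grade reaction in the lead-in. The expected number unrecorded among n = 16 is 16p, and the chance of at least one is 1 - (1 - p)^n:

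| p (assumed) | Expected of 16 | At least one of 16 | At least one of first 3 |
|---|---|---|---|
| 10% | 1.6 | 0.81 | 0.27 |
| 20% | 3.2 | 0.97 | 0.49 |
| 30% | 4.8 | 0.997 | 0.66 |
| 50% | 8.0 | about 1.0 | 0.88 |

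**5. What depends on these events.** The primary safety event (13.2.1) is grade 3 or higher and related to any study treatment, and such events are recorded from the first interferon dose. The stopping boundaries in 13.2.2 count those events. No sample size, power or boundary changes.

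**6. Which symptoms overlap.** Appendix E grades CRS on fever, hypotension and hypoxia, so chills do not enter. Section 12.6.1 sends headache to the neurotoxicity (ICANS) criteria, but headache is not a domain in the Appendix E grid. Fever is the overlap that matters for grading.

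**The case against.** The strongest reply is that nothing decisive rests on the gap. No objective estimates low-grade interferon tolerability, the dose is one approved for another indication with a described profile, and most interferon doses fall inside the low-grade window. A short period of limited collection is a defensible choice. This stands as far as the endpoints go. It does not explain why the two windows start on different days for an investigational agent.

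Three stronger readings are tempting, and the documents do not support them.

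- A reader might infer that low-grade interferon toxicity is lost. It is not: 8-10 of 12 first-cycle doses are covered. What is missing is the part given without T cells.
- A reader might infer that later events will be misassigned to T cells. No section does this. Attribution is the principal investigator's judgement under 12.4, which asks about other interventions. Section 11.4 requires an interval history and examination on the day of infusion, and Appendix E excludes fever with another cause. The clinician may know what the case report form does not show.
- A reader might infer that the discontinuation rule in 11.7 lacks its data: "Occurrence of any non-pre-existing grade 3 or higher AEs / repetitive Grade 2 Adverse events deemed related to the treatment". The pre-existing qualifier belongs to grade 3 or higher events, which are recorded from the first interferon dose. The sentence goes on to except expected transient toxicities, interferon's included, and grade 2 repeats from day 0 are recorded. Only non-excepted grade 2 events within the lead-in are missing.

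It could also be proposed that lead-in events become the reference for grading CRS or neurotoxicity. That should not be done here: it would alter a grading rule that Appendix F ties to clinical management.

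**Conclusion.** The point holds as a gap in low-grade safety data, clearest in cycle 1. Between the first interferon dose and the infusion, 12.5 does not require grade 1-2 events to be recorded. The loss is a within-patient comparison that would support the attribution of fever, and with it a description of interferon's low-grade effects when given alone. Any misattribution remains a possibility that the plan leaves harder to check.

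The dose shares rest on the 12-dose course in 6.3. The expected counts rest on assumed reaction rates and on all 16 patients being treated. The gap itself rests on neither.

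**What to change.** In 12.5, start grade 1-2 recording at the first interferon gamma dose of each cycle, the same start as for grade 3-5. Align 14.2, which names only grade 3-5 events when it describes case report form content. Leave the CRS and neurotoxicity grading rules unchanged.

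The cost is about one week of extra low-grade entries per cycle for at most 16 patients. Sections 11.3 and 11.4 list no symptom assessment between the first interferon dose and day 0, so the existing day 0 history would have to ask about symptoms since that first dose. In cycle 1, 11.1 already keeps patients near the site from then. No new visit or test is needed.

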12.6 Expected Grade 3-4 Adverse Events

Avelumab, pembrolizumab, interferon gamma, and T cell infusions each have associated, expected, transient toxicities that will not be considered grounds for therapy discontinuation nor counted as adverse events for determination of treatment safety/dose limiting toxicity. These will however be appropriately logged and reported as with any other grade 3-4 toxicity below.

12.6.1 Expected Adverse Events: T cell infusion

The following toxicities are expected adverse events and will not be counted as dose limiting toxicities

- Grade 3-4 lymphopenia.

Rationale: Lymphopenia is an expected toxicity of T cell therapy, even without lymphodepleting chemotherapy.^{87,88} This was also observed in prior trials of endogenous T cells in MCC (**Table 2**), where 6/12 patients had grade 3 or 4 lymphopenia. In most cases, lymphopenia had onset of 24-72 hours after T cell infusion and in all cases lymphopenia had recovered to grade 2 or less by day +28 after T cell infusion.

T cell activation has a known constellation of inflammatory responses that is well defined. This is an expected toxicity of cellular therapy as the immune system activates and seeks to immunologically reject tumor. There are defined guidelines for cytokine release syndrome (CRS) as well as immune-effector cell-associated neurotoxicity syndrome (ICANS).

Therefore, the following toxicities will be evaluated under consensus evaluations for CRS and/or ICANS if suspected due to T cell activation (**Appendix E**)⁷⁹ and thus individual toxicities will not be considered DLT unless CRS and/or ICANS is grade III or higher

- Fevers, hypoxia, hypotension: Fevers, hypoxia, hypotension suspected to be related to cytokine release syndrome and occurring within 28 days after T cell infusion will be graded in aggregate under the Lee et al cytokine release syndrome consensus guidelines (**Appendix E**). The individual components will NOT count as DLTs based on CTCAE criteria.
- Tachycardia, flushing, tachypnea: Tachycardia and flushing often accompany CRS as a result of the fevers and inflammation and are included in some grading criteria. Therefore, tachycardia (so long as sinus), flushing, and tachypnea will not individually count as DLTs if suspected to be due to CRS and CRS will instead be graded with Lee criteria, as above.

- Headache, confusion, seizure, delirium, and encephalopathy will be evaluated under neurotoxicity/ICANS criteria if occurring within 28 days of T cell infusion (**Appendix E**), and ICANS criteria will be used for grading/DLT determination.

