7.2 Management of toxicity associated with interferon gamma

Patients will be premedicated with acetaminophen 650 mg prior to each dose.

Mild acute administration reactions should be managed with antipyretics, antihistamines, and anti-emetics as clinically appropriate, and these may be added to prophylaxis for future doses.

Corticosteroids should be avoided. Appropriate emergency medications (e.g., epinephrine, diphenhydramine, etc.) should be readily available during administration and institutional guidelines should be followed for the treatment of anaphylaxis.

Fever and flu like symptoms should be treated with antipyretics as needed.

Local reactions can be managed by choosing alternate sites.

Severe symptoms or those involving hypoxemia or hypotension, particularly following T cell infusion, should be treated as presumptive cytokine release syndrome and treated as below.

Doses may be held or treatment discontinued due to intolerable side effects or grade III or higher adverse events attributable to interferon gamma. Adverse events attributable to T cell infusion (e.g. cytokine release syndrome) will be assumed to be synergistic with interferon gamma, and interferon gamma will be held in these cases.

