13.2 Primary Endpoint: Safety

13.2.1 Definition of treatment related adverse event

For the purposes of statistical analysis and estimation of toxicity rate, a safety event will be any grade 3 or higher adverse event determined to be possibly, probably, or definitely secondary to any of the study treatments, except as expected in **Sections 12.5 and 12.6**. Please see **Section 12.1** for adverse event definition.

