Seizure	N/A	N/A	Any clinical seizure focal or generalized that resolves rapidly or nonconvulsive seizures on EEG that resolve with intervention	Life-threatening prolonged seizure (> 5 min); or Repetitive clinical or electrical seizures without return to baseline in between
Motor findings[‡]	N/A	N/A	N/A	Deep focal motor weakness such as hemiparesis or paraparesis
Elevated ICP/ cerebral edema	N/A	N/A	Focal/local edema on neuroimaging [§]	Diffuse cerebral edema on neuroimaging; decerebrate or decorticate posturing; or cranial nerve VI palsies; or papilledema; or Cushing's triad

ICANS grade is determined by the most severe event (ICE score, level of consciousness, seizure, motor findings, raised ICP/cerebral edema) not attributable to any other cause; for example, a patient with an ICE score of 3 who has a generalized seizure is classified as grade 3 ICANS.

N/A indicates not applicable.

* A patient with an ICE score of 0 may be classified as grade 3 ICANS if awake with global aphasia, but a patient with an ICE score of 0 may be classified as grade 4 ICANS if unarousable.

[†] Depressed level of consciousness should be attributable to no other cause (eg, no sedating medication).

[‡] Tremors and myoclonus associated with immune effector cell therapies may be graded according to CTCAE v5.0, but they do not influence ICANS grading.

[§] Intracranial hemorrhage with or without associated edema is not considered a neurotoxicity feature and is excluded from ICANS grading. It may be graded according to CTCAE v5.0.

Neurotoxicity/ICANS grading will be as per ASTCT CRS Consensus Grading. Table reprinted for reference from the guideline of Lee et al, 2019 ASTCT Consensus Grading for Cytokine Release Syndrome and Neurologic Toxicity Associated with Immune Effector Cells, Biol Blood Marrow Transplant 25(2019) 625-638

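### Section 12.6.1 grades headache by ICANS, which has no headache domain, so a severe isolated headache drops out of the primary safety count; a first afebrile suspected-CRS event has a narrower gap of the same kind

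*Combined protocol and SAP*

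**What the plan says.** Section 13.2.1 defines a primary safety event as "any grade 3 or higher adverse event determined to be possibly, probably, or definitely secondary to any of the study treatments", apart from the exceptions in 12.5 and 12.6. Section 12.6 says that its expected toxicities are neither grounds for stopping therapy "nor counted as adverse events for determination of treatment safety/dose limiting toxicity", and then adds: "These will however be appropriately logged and reported as with any other grade 3-4 toxicity below".

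Section 12.6.1 lists symptoms that go to the CRS and ICANS scales when T cell activation is suspected. Taken singly they are not DLTs unless the CRS or ICANS itself reaches grade III.

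- Neurological symptoms: "Headache, confusion, seizure, delirium, and encephalopathy will be evaluated under neurotoxicity/ICANS criteria if occurring within 28 days of T cell infusion". ICANS criteria then settle both the grade and DLT status.
- Fever, hypoxia and hypotension suspected to be CRS are graded together on the CRS scale. "The individual components will NOT count as DLTs based on CTCAE criteria".

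In Appendix E, "ICANS grade is determined by the most severe event (ICE score, level of consciousness, seizure, motor findings, raised ICP/cerebral edema"), and every CRS grade carries a temperature of at least 38°C. A footnote relaxes the fever condition: "In patients who have CRS then receive antipyretic or anticytokine therapy such as tocilizumab or steroids, fever is no longer required" for grading later severity. Section 12.3 folds CRS components into the CRS grade only while timing and clinical picture fit CRS, and grades all other events by CTCAE v5.0.

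**The concern.** A rule that replaces one grading scale by another needs the second scale to return a grade for everything sent to it. Here it does not. Headache is named in the ICANS bullet but cannot produce an ICANS grade. Appendix E names CTCAE as a possible grading route for tremor, myoclonus and intracranial hemorrhage, but says nothing about headache. The CRS scale likewise gives no grade to a first episode that has no fever.

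An event lost this way can only make the regimen look safer. The count feeds the 40% toxicity criterion and the 13.2.2 boundary, and similar counts drive the three-patient decisions in Section 4.4, where one patient separates proceeding (1 of 3) from suspension (2 of 3).

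**Working it through.** **1. Headache.** Take an isolated headache that would be grade 3 under CTCAE, within 28 days of infusion and suspected to come from T cell activation.

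- 12.6.1 sends it to ICANS for grade and DLT status.
- Appendix E needs an ICE score, depressed consciousness, a seizure, a motor finding or raised ICP/edema. None is present, so there is no ICANS grade, and grade III is not reached.
- 12.6 applies its exceptions to treatment safety as well as to DLTs, and 13.2.1 adopts them. Read literally, the event counts as zero.
- The clinical-picture condition in 12.3 concerns CRS components, so it does not bring headache back.

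**2. Hypotension or hypoxia without fever.** Three cases need separating.

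| Case | Route | Counted? |
|---|---|---|
| Not suspected to be CRS, or picture judged not to fit CRS | CTCAE v5.0 by 12.3 | Yes, if grade 3 or higher and related |
| CRS already present and treated with an antipyretic or anticytokine agent | CRS scale, fever waived by the Appendix E footnote | Yes, if CRS grade 3 or higher |
| First episode, no fever, still suspected to be CRS | CRS scale gives no grade; 12.6.1 sets the CTCAE grade aside | No |

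Only the third case is a gap. It is plausible for two reasons. Section 7.2 has severe symptoms with hypoxemia or hypotension, particularly after T cell infusion, handled as presumptive CRS, with no fever condition. The same section says "Patients will be premedicated with acetaminophen 650 mg prior to each dose" of interferon gamma, while the footnote covers only antipyretics given once CRS exists. Under 6.3 interferon gamma runs for 4 weeks from 5 to 7 days before infusion, that is to about day 21 to 23 (28 − 7 to 28 − 5).

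**3. The plan's own figures.** Inputs from 13.2.2: suspend at 2/2, 3/3-4, 4/5-6, 5/7-8, 6/9-10, 7/11-12, 8/13-14 or 9/15-16, with at most 16 patients. Let f_n(k) be the probability of k events after n patients without earlier suspension, and b_n the boundary. Then f_n(k) = p·f_{n−1}(k−1) + (1−p)·f_{n−1}(k), where paths with k ≥ b_n are removed at each n, and P(suspend) is the total removed.

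- p = 0.20: 0.062 (plan: about 0.06)
- p = 0.60: 0.847 (plan: about 0.84)

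The stated figures reproduce, for the boundary alone.

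**4. Illustration of a loss.** The documents give no rate for ungraded events. Assume that a share s of patients with a true safety event have only an ungraded one. The counted rate is then true rate × (1 − s).

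| True rate | s | Counted rate | P(suspend) |
|---|---|---|---|
| 60% | 0 | 60% | 0.847 |
| 60% | 5% | 57% | 0.791 |
| 60% | 1/12 (5 points) | 55% | 0.748 |
| 60% | 10% | 54% | 0.726 |
| 60% | 20% | 48% | 0.578 |
| 50% | 0 | 50% | 0.629 |
| 50% | 5% | 47.5% | 0.565 |
| 50% | 10% (5 points) | 45% | 0.501 |
| 50% | 20% | 40% | 0.377 |

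For a three-patient rule that uses the same count, P(at least 2 of 3) = 3p²(1−p) + p³. This falls from 0.648 at 60% to 0.575 at 55%, and from 0.500 at 50% to 0.425 at 45%.

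**The case against.** Using a consensus scale in place of component-by-component CTCAE grading is deliberate and explained in 12.3 and 12.6.1. Section 12.3 can also be read as already returning afebrile events to CTCAE: if fever is part of every CRS grade, an episode without fever does not fit the CRS picture. That reading is reasonable, but it depends on the investigator withdrawing the suspicion of CRS. 12.6.1 turns on suspicion, and no section says what happens when suspicion remains and the scale yields nothing.

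The events are not hidden. They are logged (12.6), and under 14.2 the DSMB reviews all CTCAE grade 3 or greater toxicities and decides on part II. The synopsis lets the PI declare any other toxicity a DLT. The part I suspension sentence in 4.4 states no 12.6 exception, whereas the part II sentence does, so a lost event need not change the part I decision. All of this stands as protection for patients. It does not repair the endpoint, because 13.2.1 does not draw on the synopsis DLT list or on DSMB judgement.

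The numbers affected are probably small. Section 7.1 lists headache as a common effect of interferon gamma, and 12.6.2 already excepts transient flu-like reactions to it. The count is per patient, so any other qualifying event restores that patient. Section 2.1.6 reports only grade 1-2 CRS and transient lymphopenia in 24 patients given a different TCR product, and 7.7 says neurotoxicity has not been reported with transgenic TCR therapy. This limits the size of the problem but does not remove it.

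**Conclusion.** The headache gap is real on the plain text: 12.6.1 assigns the symptom to a scale that cannot grade it, and 12.6 and 13.2.1 carry the result into a primary endpoint. The CRS gap is real but confined to a first afebrile episode still suspected to be CRS.

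Three stronger readings are not supported:

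- A reader might infer that any hypotension or hypoxia without fever scores zero. Section 12.3 and the Appendix E footnote cover the other cases.
- A reader might infer that these events vanish or may not be CTCAE-graded at all. They are logged, reported and reviewed; what is excluded is counting them.
- A reader might cite Section 7.10, on hypotension without fever, as showing that afebrile CRS is expected. That section concerns adrenal toxicity.

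The direction of any error is known: towards looking safer. Its size is not. The falls from 0.85 to 0.75 (true rate 60%) and from 0.63 to 0.50 (true rate 50%) rest on an assumed 5-point loss and show how sensitive the boundary is. They do not estimate what this wording will cost. The point merits correction because the rule as written gives a wrong count and the repair is small.

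**What to change.** Make one edit and leave the lists in 12.6.1 unchanged. Add at the end of that section:

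> A listed event that receives no CRS or ICANS grade under Appendix E (for example, headache alone, or a first episode of hypotension or hypoxia without fever) is graded by CTCAE v5.0 and counts for DLT determination and for Section 13.2.1 on that grade, unless another exception in 12.6 applies.

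Headache that accompanies an ICANS feature is still graded as ICANS, and the interferon gamma and checkpoint inhibitor exceptions stay as they are. The sentence concerns grading and counting only and sets no rule for managing patients. The cost is one sentence and a possibly slightly higher observed toxicity rate. The boundary and sample size do not change.
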